11.2 Analysis of Adverse Events

Adverse events (AEs) will be coded using the Medical Dictionary for Regulatory Activities (MedDRA). The actual version of the MedDRA coding dictionary will be noted in the clinical study report.

HIV co-infected subjects are allowed to enroll into the study and the AIDS-associated opportunistic infections will be flagged on the AE eCRF and in the AE database, which be excluded from all AE summary tables and listings. A separate listing of AIDS-associated opportunistic infections will be generated for the HIV co-infected subjects if there are HIV co-infected subjects enrolled under such conditions.

11.2.1 Treatment-Emergent Adverse Events

Treatment-emergent AEs are defined as any adverse event with an onset date that is after the first dose of study drug and no more than 30 days after the last dose of study drug. Events where the onset date is the same as the study drug start date are assumed to be treatment-emergent. If an incomplete onset date was collected for an adverse event, the event will be assumed to be treatment-emergent, unless there is other evidence that confirms that the event was not treatment-emergent (e.g., the event end date was prior to the study drug start date).

11.2.2 Tabulations of Treatment-Emergent Adverse Events

The number and percentage of subjects in each age group and overall with treatment-emergent AEs will be tabulated by primary MedDRA System Organ Class (SOC) and preferred term (PT). The SOC will be presented in alphabetical order, and the PTs will be presented in alphabetical order within each SOC.

Subjects reporting more than one AE for a given PT will be counted only once for that term (most severe/highest grade incident for the severity tables and most related incident for the relationship tables). Subjects reporting more than one AE within a SOC will be counted only once for that SOC. Subjects reporting more than one AE will be counted only once in the overall total.

Adverse Event Overview

An overview of AEs will be presented for each age group and overall consisting of the number and percentage of subjects experiencing at least one event for each of the following AE categories:

- Any treatment-emergent AE;
- Treatment-emergent AEs with a "reasonable possibility" of being related to DAAs (glecaprevir/pibrentasvir);
- Treatment-emergent AEs of grade 3 or higher;
- Treatment-emergent adverse events of Grade 3 or higher with a "reasonable possibility" of being related to DAA (glecaprevir/pibrentasvir);
- Serious treatment-emergent AEs;
- Serious treatment-emergent AEs with a "reasonable possibility" of being related to DAAs (glecaprevir/pibrentasvir);
- Treatment-emergent AEs leading to discontinuation of study drug;
- DAA-related treatment-emergent AEs leading to discontinuation of study drug;
- Serious treatment-emergent AEs leading to discontinuation of study drug;
- Treatment-emergent AEs leading to interruption of study drug;
- Treatment-emergent AEs leading to death;
- Deaths.

Adverse Events by SOC and PT

The following summaries of AEs by SOC and PT will be generated by age group and overall:

- Treatment-emergent adverse events;
- Treatment-emergent AEs with a "reasonable possibility" of being related to DAAs (glecaprevir/pibrentasvir);
- Treatment-emergent AEs of Grade 3 or higher;

- Treatment-emergent AEs of Grade 3 or higher with a "reasonable possibility" of being related to DAA (glecaprevir/pibrentasvir);
- Serious treatment-emergent AEs;
- Serious treatment-emergent AEs with a "reasonable possibility" of being related to DAAs (glecaprevir/pibrentasvir);
- Treatment-emergent AEs leading to discontinuation of study drug;
- DAA-related treatment-emergent AEs leading to discontinuation of study drug;
- Serious treatment-emergent AEs leading to discontinuation of study drug;
- Treatment-emergent AEs leading to interruption of study drug;
- Treatment-emergent AEs leading to death.

A listing of treatment-emergent AEs grouped by body system and preferred term with subject numbers will be created for each age group.

Adverse Events by PT

The number and percentage of subjects experiencing treatment-emergent AEs will be tabulated according to PT and sorted by overall frequency across the four age groups. Similar summaries will be provided for Grade 3 or higher treatment-emergent AEs, DAA related treatment-emergent AEs, DAA-related Grade 3 or higher treatment-emergent AEs, and DAA related treatment-emergent serious AEs.

Adverse Events by Maximum Severity Grade Level

Treatment-emergent AEs and DAA-related treatment-emergent AEs will be summarized by maximum severity grade level of each PT. Each AE will be assigned a grade level (grade 1, 2, 3, 4, or 5) by the investigator. If a subject has an AE with unknown severity, then the subject will be counted in the severity grade level category of "unknown," even if the subject has another occurrence of the same event with a severity present. The only exception is if the subject has another occurrence of the same AE with the highest grade level (grade 5). In this case, the subject will be counted under the "Grade 5" category.

Adverse Event by Maximum Relationship

Treatment-emergent AEs also will be summarized by maximum relationship of each PT to study drug (DAA), as assessed by the investigator. If a subject has an AE with unknown relationship, then the subject will be counted in the relationship category of "unknown," even if the subject has another occurrence of the same event with a relationship present. The only exception is if the subject has another occurrence of the same adverse event with a relationship assessment of "Reasonable Possibility." In this case, the subject will be counted under the "Reasonable Possibility" category.

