### 6.1.3 Relationship to Study Drug

The investigator will use the following definitions to assess the relationship of the adverse event to the use of study drug:

Reasonable Possibility	An adverse event where there is evidence to suggest a causal relationship between the study drug and the adverse event.
No Reasonable Possibility	An adverse event where there is no evidence to suggest a causal relationship between the study drug and the adverse event.

For causality assessments, events assessed as having a reasonable possibility of being related to the study drug will be considered "associated." Events assessed as having no reasonable possibility of being related to study drug will be considered "not associated." In addition, when the investigator has not reported a causality or deemed it not assessable, AbbVie will consider the event associated.

For serious adverse events, if an investigator's opinion of "no reasonable possibility of being related to study drug" is given, an "Other" cause of event must be provided by the investigator.

[figure not shown]

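### In the SAP's maximum-severity AE tables one ungraded occurrence overrides a known Grade 1 to 4; a lesser, parallel gap concerns missing causality

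*SAP*

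**What the plan says.** **Severity.** The opening of SAP 11.2.2 sets a general rule for repeated events. A subject is counted once per preferred term, at the worst grade for severity tables and at the most related assessment for relationship tables. Two severity tables follow: "Treatment-emergent AEs and DAA-related treatment-emergent AEs will be summarized by maximum severity grade level of each PT". For these the SAP adds: "If a subject has an AE with unknown severity, then the subject will be counted in the severity grade level category of" *unknown*, even if another occurrence of the same event has a grade. The only exception is another occurrence at Grade 5. The same section also plans separate Grade 3 or higher outputs in the overview, by system organ class and preferred term, and by preferred term alone.

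**Relationship.** One table is "summarized by maximum relationship of each PT to study drug (DAA), as assessed by the investigator". Its missing-data rule is parallel: "If a subject has an AE with unknown relationship, then the subject will be counted in the relationship category of" *unknown*, unless another occurrence of the same event is rated a reasonable possibility. Protocol 6.1.3 says that "when the investigator has not reported a causality or deemed it not assessable, AbbVie will consider the event associated".

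**Related-AE summaries.** Some outputs are defined by a reasonable possibility of relation to the DAAs. Others use the label DAA-related, for example "DAA-related treatment-emergent AEs leading to discontinuation of study drug" and the preferred-term tables for "DAA related treatment-emergent AEs, DAA-related Grade 3 or higher treatment-emergent AEs, and DAA related treatment-emergent serious AEs". The SAP does not define that label.

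**The concern.** A table of maximum severity should show the worst grade known for each subject and term. Here a recorded Grade 4 can be displaced by a second occurrence that nobody graded. The same subject is still counted in the Grade 3 or higher tables, so the two sets of outputs need not reconcile, and the SAP plans no listing that would explain the difference.

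On causality, the protocol classes an event with no usable assessment as associated. The SAP's relationship table shows it as *unknown*. The summaries defined by reasonable possibility, read literally, leave it out, so no related-AE output is stated to apply protocol 6.1.3.

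Safety and tolerability by age group is a primary objective (protocol 4.1), and protocol 8.1.5.1 promises tabulation by grade and by relationship. Protocol 8.1.5 nevertheless calls AE rates secondary safety endpoints, and no hypothesis test depends on these tables. What is at stake is whether the safety tables can be read and reconciled.

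**Working it through.** The plan states no figure to reproduce. The check applies each written rule to every pattern that contains a missing value.

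**Severity.** One subject, one preferred term; rules from SAP 11.2.2.

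| Occurrences | Maximum-severity table as written | Grade 3 or higher tables | Highest known grade |
|---|---|---|---|
| Grade 1 + ungraded | unknown | not counted | 1 |
| Grade 2 + ungraded | unknown | not counted | 2 |
| Grade 3 + ungraded | unknown | counted | 3 |
| Grade 4 + ungraded | unknown | counted | 4 |
| Grade 5 + ungraded | Grade 5 | counted | 5 |
| ungraded only | unknown | not counted | none |

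The known grade is displaced in 4 of the 5 mixed patterns. In 2 of those 4 (Grades 3 and 4) the maximum-severity table disagrees with the Grade 3 or higher tables for the same subject.

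**Causality.** SAP 11.2.2 against protocol 6.1.3.

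| Occurrences | SAP maximum-relationship table | Protocol 6.1.3 |
|---|---|---|
| missing only | unknown | associated |
| missing + no reasonable possibility | unknown | associated |
| missing + reasonable possibility | reasonable possibility | associated |

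The two differ in 2 of 3 patterns and agree wherever one occurrence is rated a reasonable possibility.

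**Other related-AE outputs.** Defined by reasonable possibility: 3 overview rows + 3 tables by system organ class and preferred term = 6. Labelled DAA-related: 1 overview row + 1 table by system organ class and preferred term + 3 preferred-term tables + 1 maximum-severity table = 6. Total 12.

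**Scale.** Planned sizes are from protocol 5.1: 44 in Part 1 and 81 in Part 2, together 125. One reclassified subject moves a percentage by:

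- overall: 1/125 = 0.8 points;
- Part 1: 1/44 = 2.3 points;
- a Part 2 age group: 81/3 = 27 if the three groups are equal (an assumption), and 1/27 = 3.7 points.

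These are weights per affected subject. The pattern counts above describe rules, not frequencies. The documents give no rate of missing grade or causality, so the expected number of affected subjects cannot be calculated.

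**The case against.** **The severity rule is a coherent convention.** If one occurrence is ungraded, the true maximum is unknown unless another is already Grade 5, which is exactly the SAP's exception; a specific rule may also qualify a general one. That logic stands. But the known grade is a lower bound that the table discards while the Grade 3 or higher tables use it. Showing that bound invents no data.

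**The causality rule may not be a departure.** Protocol 6.1.3 sits in the section on assessing and reporting events and says how the sponsor will regard them. The SAP table is labelled as the investigator's assessment, and its *unknown* row is visible. Protocol 8.1 also says that nothing is imputed in efficacy or safety analyses except for SVR, and calling a missing causality related could be seen as imputation. Much of this stands, and it is why the investigator table should stay. It does not settle the related-AE summaries: protocol 6.1.3 is the specific rule on causality, and SAP 11.2.1 already assumes that events with incomplete onset dates are treatment-emergent absent contrary evidence.

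**Stronger readings that the documents do not support:**

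- *Severe events disappear.* They do not; the Grade 3 or higher tables still count them.
- *The sponsor failed to declare a departure in SAP 12.1.* This cannot be judged. SAP 3.0 says that the SAP was written to Amendment 1 of 25 July 2017, which is not among the supplied documents.
- *The undefined DAA-related label implies a second causality rule and conflicting counts.* Protocol 6.1.3 has only one positive category, so the label is most naturally shorthand for reasonable possibility. This is an editorial matter.

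**Conclusion.** The severity point holds: the missing-grade rule departs from the SAP's own general rule and lets the maximum-severity and Grade 3 or higher tables disagree for the same subject. The causality point holds in a narrower form: the SAP does not say how the protocol's classification of missing causality enters the related-AE summaries, nor how that fits with the no-imputation statement in protocol 8.1.

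The effect is descriptive and probably very small. Protocol 6.1 has the investigator record severity and relationship for each event, protocol 10.2 provides for review of case report forms for completeness, and SAP 4.4 has the data cleaned before each lock. The judgement of size rests on those steps working, since no missing rate is given. It is worth correcting because the change is cheap; it does not threaten the trial's conclusions.

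**What to change.** In SAP 11.2.2:

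1. **Maximum severity.** Show the highest known grade per preferred term. Reserve *unknown* for subjects with no graded occurrence of that term. Footnote the number of subjects who also had an ungraded occurrence.
2. **Causality.** Keep the investigator-assessed maximum-relationship table with its *unknown* row. In the related-AE summaries, count events with unreported or non-assessable causality as related under protocol 6.1.3, and footnote the number so assigned. State that this is the protocol's classification rule, so that it is reconciled with protocol 8.1.
3. **Wording.** As an editorial clean-up, define DAA-related once and use one term throughout.

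The cost is a few sentences, a small derivation change and the footnotes; data collection is unaffected. There are two downsides. The highest known grade may understate the true maximum, which the footnote discloses, and related counts may rise slightly.

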11.2.3 Adverse Events of Special Interest

Adverse events of special interest included the following:

- Hepatic decompensation/hepatic failure events, identified using the AbbVie Product MedDRA Query (PMQ) for "Hepatic Decompensation and Hepatic Failure."
- Hepatocellular carcinoma events, identified using the preferred terms of hepatocellular carcinoma, hepatic neoplasm, hepatic cancer, hepatic cancer metastatic, and hepatic cancer recurrent.

For the hepatic decompensation/hepatic failure AE of special interest, the number and percentage of subjects experiencing at least one treatment-emergent AE in the search will be presented by SOC and preferred term and across all SOCs/preferred terms. In addition, a by-subject listing of treatment-emergent AEs meeting the search criterion will be provided.

For the hepatocellular carcinoma AE of special interest, the number and percentage of subjects experiencing at least one post-baseline AE in the search will be presented by SOC and preferred term and across all SOCs/preferred terms. In addition, a by-subject listing of all post-baseline (i.e., including both treatment-emergent and non-treatment emergent) AEs meeting the search criterion will be provided.

11.2.4 Listing of Adverse Events

The following listings of AEs will be prepared:

- All serious AEs (from the time the subject signed the study-specific informed consent through the end of the study),
- Treatment-emergent serious AEs,
- Treatment-emergent AEs leading to death,
- Treatment-emergent AEs leading to discontinuation of study drug,
- Treatment-emergent AEs leading to study drug interruption.
- Treatment-emergent AEs in each of the AEs of special interest categories.

11.3 Analysis of Laboratory Data

Data collected from the central and local laboratories, including additional laboratory testing due to an SAE, will be used in all analyses.

11.3.1 Variables and Criteria Defining Abnormality

Hematology variables include: hematocrit, hemoglobin, red blood cell (RBC) count, white blood cell (WBC) count, neutrophils, bands, lymphocytes, monocytes, basophils, eosinophils, platelet count, reticulocyte count, prothrombin time (PT), international normalized ratio (INR), and activated partial thromboplastin time (aPTT).

Chemistry variables include: blood urea nitrogen (BUN), creatinine, total bilirubin, direct and indirect bilirubin, alanine aminotransferase (ALT), aspartate aminotransferase (AST), alkaline phosphatase, sodium, potassium, calcium, inorganic phosphorus, total protein, glucose, albumin, chloride, bicarbonate, magnesium, , gamma-glutamyl transferase (GGT), alpha fetoprotein, fibrotest, APRI, creatinine clearance (calculated using Cockcroft-Gault), and glomerular filtration rate (GFR) for creatinine adjusted for body surface area (BSA).

Urinalysis variables include: specific gravity and pH.

The central lab calculates the estimated creatinine clearance (CrCl) based on the following Cockcroft-Gault formula:

$$\text{CrCl (mL/min)} = [(140 - \text{age}) \times (\text{weight in kg}) \times (0.85 \text{ if female})] / [\text{serum creatinine (mg/dL)} \times 72].$$

The central lab calculates the GFR for creatinine adjusted for BSA based on the following formula:

$$\text{GFR for serum adjusted for BSA (mL/min/1.73 m}^2\text{)} = \text{CrCl (mL/min)} \times 1.73 / \{[(\text{weight in kg}) \times (\text{height in meter})]^{0.5} / 60\}.$$

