**Table 8. Clinical Laboratory Tests**

Hematology	Clinical Chemistry	Additional Tests
Hematocrit	Blood Urea Nitrogen (BUN)	Anti-HCV Ab c
Hemoglobin	Creatinine	Anti-HIV Ab c
Red Blood Cell (RBC) count	Total bilirubin a,b	FSH f
White Blood Cell (WBC) count	Direct and indirect bilirubin	Urine and Serum
Neutrophils	Serum glutamic-pyruvic	Human Chorionic
Bands, if detected	transaminase (SGPT/ALT)	Gonadotropin (hCG) g
Lymphocytes	Serum glutamic-oxaloacetic	HCV RNA
Monocytes	transaminase (SGOT/AST)	HCV genotype and subtype c
Basophils	Albumin a	HBsAg c,h
Eosinophils	Alkaline phosphatase	Anti-HBcIgM h
Platelet count (estimate not acceptable)	Sodium	Anti-HBc Total c,h
Prothrombin Time/INR a	Potassium	Anti-HBs c,h
Activated partial thromboplastin time (aPTT)	Calcium	HBV DNA k
	Inorganic phosphate	Anti-HAVIgM h
	Total protein	Anti-HAVIgG h
	Glucose	Anti-HEVIgG h
	Bicarbonate/CO 2	Anti-HEVIgM h
	Chloride	HEV RNA h
	Magnesium	HIV-1 RNA i
	Creatinine clearance	Flow Cytometry i
	(Cockcroft-Gault calculation for subjects ≥ 12 years old and Schwartz formula for those < 12 years old)	HIV Resistance j
	Alpha2-macroglobulin b	
	Gamma-glutamyl transferase (GGT) b	
	Haptoglobin b	
	Apolipoprotein A1 b	
	Alpha fetoprotein	
	Gamma-globulin d	
	Hyaluronate d	
	eGFRJ (MDRD modified) e	
Urinalysis		
Specific gravity		
Ketones		
pH		
Protein		
Glucose		
Blood		
Urobilinogen		
Bilirubin		
Leukocyte esterase		
Microscopic (reflex)		

- a. Also a component of the Child-Pugh Assessment.
- b. Also a component of FibroTest.
- c. Performed at Screening.
- d. For Japan subjects only: Component of Discriminant Score and collected only if needed during the Screening Period.
- e. eGFR calculated by the MDRD formula, modified for the Japanese population.
- f. Performed only at Screening. FSH will be taken for female subjects aged ≥ 9 to <18 years old.

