3.0 Introduction

This statistical analysis plan (SAP) describes the statistical analyses to be completed by the AbbVie Statistics and Statistical Programming Departments, or designee, for Study M16-123.

Study M16-123 assesses the pharmacokinetics, safety, and efficacy of glecaprevir/pibrentasvir (GLE/PIB) in pediatric subjects with chronic hepatitis C virus (HCV) genotypes 1 – 6 chronic Infection with or without compensated cirrhosis and with or without HIV infection, who are HCV treatment-naïve or interferon/pegylated interferon (IFN), ribavirin (RBV) and/or sofosbuvir (SOF) treatment-experienced subjects.

This SAP (Version 1.0) provides details to further elaborate the statistical methods outlined in Clinical Study Protocol M16-123 Amendment 1 dated 25 July 2017, and describes analysis conventions to guide the statistical programming. Analyses will be performed using SAS[®] Version 9.4 (SAS Institute, Inc., Cary, NC) or later under the UNIX operating system.

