- For treatment-experienced subjects, type of non-response to previous treatment (on-treatment nonresponder or breakthrough, post-treatment relapse, or unknown/other);
- Baseline fibrosis stage (equivalent to Metavir F0 – F1, F2, F3, or F4);
- Baseline cirrhosis status (cirrhotic or non-cirrhotic)
- Baseline HCV RNA level ($< 1,000,000 \geq 1,000,000$ to $< 2,000,000, \geq 2,000,000$ IU/mL);
- Baseline platelet count (< 90 or $\geq 90 \times 10^9/L$);
- Baseline albumin (< 35 or ≥ 35 g/L);
- Baseline eGFR ($< 30, \geq 30$ to $< 60, \geq 60$ to $< 90, \geq 90$ mL/min/1.73 m²);
- HIV co-infected subjects (yes/no);
- History of bleeding disorders (yes/no);
- History of depression or bipolar disorder (yes/no);
- Injection drug use (yes, within last 12 months; yes, more than 12 months ago; or no);

- Subject on stable opiate substitution (yes/no);
- Nicotine use (user, ex-user, or non-user);
- Alcohol use (drinker, ex-drinker, or non-drinker);
- Concomitant use of Proton Pump Inhibitors (PPIs).
- Concomitant use of Statins (yes/no);

In addition, for cirrhotic subjects, the following will be summarized:

- Baseline Child-Pugh score (5, 6, or > 6),
- Baseline alpha fetoprotein (< 20 or \geq 20 ng/mL),

For treatment experienced subjects, any regimen that contains SOF with or without IFN or RBV is SOF-based. Otherwise, any regimen that contains IFN with or without RBV is IFN-based.

Any concomitant medication coded to the WHO Drug Dictionary ATC code of A02BC will be counted as a PPI. Any concomitant medication coded to the WHO Drug Dictionary ATC code of C10AA or C10BX will be counted as a statin.

Baseline fibrosis stage is defined for subjects with non-missing liver biopsy scores, FibroScan scores, or FibroTest scores. Only one score will be used to categorize each subject even if a subject has more than one score recorded. If a biopsy score is present, then it will be used to categorize the subject, regardless of the FibroScan/FibroTest score. Similarly, if a FibroScan score is present along with a FibroTest score, then the FibroScan score will be used to categorize the subject. If biopsy and FibroScan scores are not present and more than one FibroTest result is available, then the baseline FibroTest result (i.e., last non-missing FibroTest result on or before Day 1) will be used to categorize the subject. Subjects will be categorized as F0 – F1, F2, F3, or F4 according to [Table 11](#).

Table 11. Baseline Fibrosis Stage

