12.0 Summary of Changes

12.1 Summary of Changes Between the Latest Version of the Protocol and SAP Version 1.0

1. The protocol stated to use Safety Population for Demog/baseline outputs; SAP changed these analyses to be run on ITT to align with the new HCV SAP template.
2. Protocol Section 8.1.6.2 planned shift tables for clinical laboratory values from low/normal to high and high/normal to low; SAP removed these analyses as the reference ranges won't work for the pediatric population.

3. Protocol Section 8.1.6.3 planned summary table for vital signs meeting Potentially Clinically Significant criteria; SAP removed these analyses due to the criteria are not applicable to pediatric population.
4. Protocol Section 8.1.3 planned change from baseline summary statistics for height, weight, and BMI z scores; SAP removed these analyses as the summary of the z scores at each applicable visit is sufficient.
5. Updates were made to the subgroup efficacy analysis section to be consistent across the HCV glecaprevir/pibrentasvir program.

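### SAP 11.3.1 prints a body-surface-area term that is 10 times too small and gives Cockcroft-Gault without an age limit, while protocol Table 8 specifies Schwartz under 12

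*SAP*

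**What the plan says.** SAP 11.3.1 names the two renal variables as "creatinine clearance (calculated using Cockcroft-Gault), and glomerular filtration rate (GFR) for creatinine adjusted for body surface area (BSA"). It prints one Cockcroft-Gault formula, with no age restriction and no alternative. For the second variable it states: "The central lab calculates the GFR for creatinine adjusted for BSA based on the following formula". That formula is clearance × 1.73 divided by a BSA term, reported in mL/min/1.73 m². In the BSA term, weight is in kg and the remainder reads "height in meter})]^{0.5} / 60".

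Protocol Table 8 splits the clearance method by age: Cockcroft-Gault from 12 years, and "Schwartz formula for those < 12 years old". It also lists a separate analyte for Japan, "eGFRJ (MDRD modified").

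These variables are used in three places:
- SAP 11.3.2 summarises each laboratory parameter by age group.
- SAP Table 15 grades unindexed creatinine clearance, with Grade 2 starting below 60 mL/min.
- SAP 7.1 lists "Baseline eGFR" with cut-offs at 30, 60 and 90 mL/min/1.73 m² but does not define it.

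SAP 12.1 records a laboratory change ("Protocol Section 8.1.6.2 planned shift tables for clinical laboratory values", which the SAP removed) but nothing on the renal formulas.

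**The concern.** There are two separate faults in one section.

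1. The denominator of the adjusted GFR has to be BSA in m², because the result is scaled to 1.73 m². With height in metres and a divisor of 60 it is not.
2. The SAP gives a single clearance formula for all four age groups, while the current protocol gives two, divided at age 12. The three Part 2 age groups, about 81 of 125 planned subjects (65%), fall on the Schwartz side.

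Safety is a primary objective. If the printed formulas are the ones used, every adjusted-GFR summary is 10-fold too high, and the clearance summaries and Table 15 clearance grades for under-12s do not follow the protocol's method. If the baseline eGFR in SAP 7.1 is the adjusted GFR of 11.3.1, its categories stop separating subjects.

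**Working it through.** **Inputs.** The formulas come from SAP 11.3.1, the cut-offs from SAP 7.1 and Table 15, and the age split from protocol Table 8. Heights, creatinine values and individual body sizes are assumptions for illustration. The factor of 10 does not depend on them.

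**BSA term.** Printed: √(kg × m)/60. Corrected: √(kg × cm)/60, which equals √(kg × m)/6. Since cm = 100 × m, the ratio is √100 = 10 at every weight and height.

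| Assumed size | Printed (m²) | Corrected (m²) |
|---|---|---|
| 12 kg, 92 cm | √(12 × 0.92)/60 = 0.055 | √(12 × 92)/60 = 0.554 |
| 25 kg, 122 cm | 0.092 | 0.920 |
| 37 kg, 140 cm | 0.120 | 1.200 |
| 70 kg, 173 cm | √(70 × 1.73)/60 = 0.183 | √(70 × 173)/60 = 1.834 |

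The formula's own reference value confirms the error. For the printed term to equal 1.73 m² at a height of 1.70 m, weight would have to be (1.73 × 60)²/1.70 ≈ 6,338 kg.

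**Effect on adjusted GFR.** Take a 17-year-old male, 65 kg, 172 cm, creatinine 0.8 mg/dL.
- Clearance = (140 − 17) × 65/(0.8 × 72) = 138.8 mL/min.
- Adjusted GFR is 1,363 mL/min/1.73 m² as printed and 136.3 with the corrected BSA.

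**Effect on the eGFR categories, if they use this variable.** The cut-offs 30/60/90 act as 3/6/9. The serum creatinine above which a male would be classed below 90 is:
- 3 y, 12 kg, 92 cm: (137 × 12/72) × 1.73/0.0554/90 = 7.9 mg/dL as printed; 0.79 corrected.
- 15 y, 55 kg, 165 cm: 11.6 mg/dL as printed; 1.16 corrected.

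**Cockcroft-Gault and Table 15 under age 12 (secondary).** The creatinine above which clearance falls below 60 mL/min is (140 − age) × weight × (0.85 if female)/(72 × 60).

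| Age, weight | Male (mg/dL) | Female (mg/dL) |
|---|---|---|
| 3 y, 12 kg | 0.38 | 0.32 |
| 4 y, 16 kg | 0.50 | 0.43 |
| 6 y, 20 kg | 0.62 | 0.53 |
| 7 y, 25 kg | 0.77 | 0.65 |
| 10 y, 37 kg | 1.11 | 0.95 |

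At an assumed 0.4 mg/dL, a 3-year-old, 12 kg boy has 137 × 12/(0.4 × 72) = 57 mL/min, which is Grade 2. Over 0.3 to 0.6 mg/dL his value runs from 76 down to 38. At 4 y, 16 kg the values at 0.4 mg/dL are 76 (male) and 64 (female); at 6 y, 20 kg they are 93 and 79. None of these four is Grade 2. So at 0.4 mg/dL only the lightest children in the youngest group are affected.

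The documents do not print the Schwartz formula, so no Schwartz value is computed and no difference in grading between the two methods is quantified.

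**The case against.** The best defence is that the SAP merely describes what the central laboratory does. Laboratory data arrive electronically from the laboratory, sponsor programmers are not told to derive GFR, and values near 1,400 to 2,000 mL/min/1.73 m² would be hard to miss at data review. This stands as a limit: nothing shows that the reported values are wrong. It does not rescue the text, which states the formula used and cannot be right.

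On the method conflict, SAP 1.0 elaborates the methods "outlined in Clinical Study Protocol M16-123 Amendment 1 dated 25 July 2017". Table 8 of that amendment is not available, so an undeclared departure at the time of writing cannot be shown, and the silence of SAP 12.1 carries less weight. The mismatch with the current protocol remains. Nor does the SAP say in words that Cockcroft-Gault applies at every age; it simply gives no other method.

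The link to baseline eGFR is conditional. The units match, but 11.3.1 does not use that term and Table 8 has a separate eGFR for Japan.

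SAP 11.3.2 also counts a grade only when it is worse than the baseline grade. A small child below 60 mL/min throughout would therefore not be counted, which narrows the Table 15 point further.

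Finally, the reach is limited. Table 15 grades unindexed clearance, so it escapes the 10-fold error. Creatinine grades expressed as multiples of the upper limit of normal, AUC and SVR12 are all untouched.

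**Conclusion.** Both parts hold. The printed BSA term is exactly one tenth of what the formula requires, so adjusted GFR as specified is 10 times too high. This is algebra and needs no assumption about the subjects. The clearance method in the SAP conflicts with the current protocol for everyone under 12.

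Whether any reported value is wrong depends on what the laboratory actually used, which the documents do not show. The effect on the baseline eGFR categories depends on which variable feeds them. The Table 15 effect is small, rests on assumed creatinine values, and arises from the method conflict, not the unit error. The faults lie in safety-variable definitions and should be corrected; they do not threaten the pharmacokinetic or efficacy conclusions.

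**What to change.** - **SAP 11.3.1, BSA term:** change height to centimetres with divisor 60, or keep metres with divisor 6.
- **SAP 11.3.1, clearance:** state the method by age as in protocol Table 8, or list and justify the departure in SAP 12.1.
- **SAP 7.1:** state which variable feeds the baseline eGFR categories, including for subjects in Japan.
- **Central laboratory:** confirm which formulas produced the transferred values, and re-derive if they match the printed ones.
- **Table 15:** once the method is settled, check that the under-12 clearance value is in mL/min, the unit of the cut-points.

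The cost is SAP text and one derivation check with the laboratory. Creatinine, height, weight, age and sex are already collected.
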